7 EVALUATION CRITERIA

An overview of the imaging trial criteria evaluated by the investigator (INV) and the Independent Blinded Readers (IBR) is provided in the [Table 2](#) below:

Table 2: Overview of imaging trial criteria

Images	Pre gadopiclenol	Pre gadobutrol	Paired gadopiclenol	Paired gadobutrol	Global matched-pairs
Lesion visualization	INV/IBR	INV/IBR	INV/IBR	INV/IBR	
Technical adequacy of images	INV/IBR	INV/IBR	INV/IBR	INV/IBR	
Number, size and location of lesions	INV/IBR	INV/IBR	INV/IBR	INV/IBR	
Diagnostic confidence	INV/IBR	INV/IBR	INV/IBR	INV/IBR	
Impact of contrast-enhanced MRI on patient treatment plan			INV	INV	
Percentage enhancement (E%) of lesion			IBR	IBR	
Lesion to Background Ratio (LBR)			IBR	IBR	
Overall diagnostic preference					IBR

INV: Investigator (on-site)

IBR: Independent Blinded Readers (off-site)

The image sets evaluated per patient are described in the [Table 3](#) below:

Table 3: Images sets per patient

Image Set Number	Type
1a	Pre images = unenhanced MRI before gadopiclenol injection
2a	Pre images = unenhanced MRI before gadobutrol injection
1b	Paired images = combined unenhanced and gadopiclenol-enhanced MRI (pre+post images)
2b	Paired images = combined unenhanced and gadobutrol-enhanced MRI (pre+post images)

 CONFIDENTIAL	Protocol No. GDX-44-011 Version No. 3.0 (including amendment 2) June 30, 2020	Page 38 / 82
---	---	--------------

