- Chemotherapy
- Radiotherapy
- Other treatment: specify

7.2.9 ***Percentage enhancement (E%) of lesion and Lesion to Background Ratio (LBR) (off-site read)***

The 2 quantitative criteria (E% and LBR) will be calculated by patient in averaging the parameter for maximum 3 most representative lesions.

 CONFIDENTIAL	Protocol No. GDX-44-011 Version No. 3.0 (including amendment 2) June 30, 2020	Page 42 / 82
---	---	--------------

- Percentage enhancement (E%) of lesion

$$E\% = \frac{SI_{post} - SI_{pre}}{SI_{pre}} \times 100$$

where SI_{post} = Signal intensity of lesion on post injection images
 SI_{pre} = Signal intensity of lesion on pre injection images

- Lesion to Background Ratio (LBR) (pre and post)

$$LBR = \frac{SI_{lesion}}{SI_b}$$

where SI_{lesion} = Signal intensity of lesion
 SI_b = Signal intensity of background (surrounding healthy tissue of the lesion)

7.2.10 *Overall diagnostic preference (off-site read)*

The evaluation will be performed in a global matched-pairs fashion (images set 1b or 2b). For each patient who received the two different IMPs, all images (paired image set 1b or 2b) from the first MR examination, labeled as examination 1, will be displayed simultaneously with the corresponding paired images from the second MR examination, labeled as examination 2.

The assessment will be performed based on 3-point scale:

- 1: When examination 1 is preferred to examination 2
- 0: When no preference is observed
- 2: When examination 2 is preferred to examination 1

IBRs need to select one or more of the following six reasons for this preference:

- Contrast enhancement was superior,
- Delineation of normal structure was better
- Delineation of at least one lesion was better
- Internal structure of lesions was better visualized
- More lesions were identified
- Diagnostic confidence was greater (specify one or more reason(s): detection of lesions, characterization of disease, assignment of a grade to disease, definition of extent of disease, or other reasons that had to be specified on the Imaging eCRF)

7.2.11 *Safety profile of gadopiclenol and gadobutrol (on-site)*

The safety assessments will be followed up by evaluating results of vital signs, injection site tolerance, clinical laboratory parameters (blood samples) and adverse events (AEs) reporting.

○ **Vital signs**

Vital signs (supine systolic and diastolic blood pressures, pulse rate) will be measured and recorded according to the following schedules:

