The patients within each batch will be ordered at random without stratification into groups of patients.

Various modalities of images from the same patient will not be presented in the same batch and the Imaging Core Laboratory will ensure an appropriate wash-out period between the evaluations of images

 CONFIDENTIAL	Protocol No. GDX-44-011 Version No. 3.0 (including amendment 2) June 30, 2020	Page 51 / 82
--	---	--------------

from two modalities (Pre and Paired images) and between two MR examinations for the same patient, to minimize recall bias.

8.4.7 ***Blinded Assessment of Images***

Imaging database including all evaluable images will be assessed by the independent readers. The reading will be performed in a strictly fully blinded manner.

No communication on patient specific image findings will be allowed between the independent readers once the blinded reviews begin.

To ensure that the centralized reading evaluations remain independent, each individual reader evaluation will be locked as they occur (i.e., it will not be possible to alter the evaluation).

8.4.8 ***Inter and Intra-reader Variability Assessment***

The assessments of inter- and intra-reader variability will be done in the final analysis.

Inter-reader variability will be evaluated on the whole set of trial patients, since each patient will be read by different readers.

Intra-reader variability: individual readers will perform repeat image evaluations of 10% of cases randomly determined. The cases used for intra-reader variability assessment will be re-introduced randomly and re-read during the course of the reading. To minimize recall bias, intra-reader variability will be assessed approximately after the first 50 cases are reviewed and no sooner than two weeks from the original reviews of these patients. Results of the original reviews for these cases will not be available to the reader. Only the first evaluation of a given image set will be included in the efficacy analysis.

8.4.9 ***Lesion tracking/Matching***

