**Percentage Enhancement of lesions (E%)**

E% is calculated from the Signal Intensity (SI) measurement of maximum 3 most representative lesions by the 3 independent off-site readers. The mean of E% will be calculated by patient using only matching lesions between GBCA

For each reader, E% will be tabulated by contrast agent groups using FAS 2. Differences between contrast agents will be tested using a Student's t-test. The models will include the contrast agent group and the period. The parameters of the general linear models with repeated measures will be estimated using the SAS® procedure Mixed. The difference between contrast agent groups in mean score and associated 95% two-sided CI will be computed.

The SAS® procedure used for the analysis will be the following:

```
proc mixed data = XXX method = REML;
  class subject GBCA period;
  model eval = GBCA period;
  repeated GBCA/subject= subject / type = cs;
  lsmeans GBCA / pdiff = control('gadobutrol') tdiff cl alpha = 0.025;
  /* The following code is needed as previous statement lsmeans does not provide the upper limit of CI */
```

CONFIDENTIAL	STATISTICAL ANALYSIS PLAN PHASE III TRIAL GDX-44-011 VERSION NO. 2.0      DATED 25 JANUARY 2021	████████ Page 39 / 57
--------------	---	--------------------------

lsmeans GBCA;  
estimate "gadopiclenol - gadobutrol" GBCA 1 -1 /cl;  
run; .

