### **Lesion to Background Ratio (LBR)**

LBR is calculated from the SI measurement of maximum 3 most representative lesions by the 3 independent off-site readers. Then, the mean of LBR will be calculated by patient and by MRI modality using only gadopiclenol-gadobutrol matching lesions. Only pre-contrast lesions which match with those gadopiclenol-gadobutrol matching lesions will be kept in the analysis and descriptive statistics.

For each reader, LBR will be tabulated by contrast agent groups on pre contrast and paired images using FAS 2.

Differences between contrast agents will be tested using a Student's t-test. The models will include the contrast agent group, the period and the unenhanced value (pre) as covariate. The parameters of the mixed models will be estimated using the SAS® procedure Mixed. The difference between contrast agent groups in mean score and associated 95% two-sided CI will be computed.

Procedure used will be the following for each off-site reader:

```
Proc mixed data = XXX method = REML;
  class subject GBCA period;
  model eval = GBCA period pre;
  repeated GBCA/subject= subject / type = cs;
  lsmeans GBCA / pdiff = control('gadobutrol') tdiff cl alpha = 0.025;
/* The following code is needed as previous statement lsmeans does not provide the upper limit of CI */
  lsmeans GBCA;
  estimate "gadopiclenol - gadobutrol" GBCA 1 -1 /cl;
run; .
```

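### The SAP's pre-contrast LBR appears to rest on lesions recorded on the separate Pre read, so records without a Pre-read match leave the LBR model

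*SAP*

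**What the plan says.** **Protocol.** Table 2 in section 7 lists which image sets the independent blinded readers use for each criterion. The LBR row reads "Lesion to Background Ratio (LBR) IBR IBR": the two entries fall under Paired gadopiclenol and Paired gadobutrol, and both Pre columns are empty. Table 3 defines the gadopiclenol Paired set as "Paired images = combined unenhanced and gadopiclenol-enhanced MRI (pre+post images", and the gadobutrol set likewise. Section 7.2.9 lists the measure as "Lesion to Background Ratio (LBR) (pre and post". Section 11.3.6 plans a Student's t-test between agents for LBR and mentions no pre-contrast covariate.

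**SAP 5.6.2, LBR.** The patient mean is formed separately for each MRI modality from lesions matched between the two agents, and is tabulated for pre-contrast and for paired images in FAS2. The restriction follows: "Only pre-contrast lesions which match with those gadopiclenol-gadobutrol matching lesions will be kept in the analysis and descriptive statistics". On the model: "The models will include the contrast agent group, the period and the unenhanced value (pre) as covariate".

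**SAP 5.6.2, E%.** "The mean of E% will be calculated by patient using only matching lesions between GBCA". No match to a Pre read is required.

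**SAP elsewhere.** FAS2 (section 5.2) requires a lesion matched between the two Paired sets for at least one off-site reader, with no Pre-read condition. Section 3.5.1 rules out imputation for efficacy.

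**The concern.** A Paired set already contains the unenhanced images. Under the protocol's layout, the pre and post LBR of a lesion can therefore be measured in one read, and every agent-matched lesion can have both values. The SAP's matching condition makes sense only if the pre value belongs to a lesion identified independently on the Pre read.

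If so, a lesion that both Paired reads found but the Pre read did not has no pre value. Because that value is a model covariate, the record cannot be used. The lesions lost this way are likely to be those that show only after contrast. LBR is a named secondary objective with a formal comparison between agents. At stake are how many FAS2 patients that comparison uses, which kind of lesion it describes, and whether outcome and covariate refer to the same lesions.

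**Working it through.** The documents state no sample size, power or count for LBR, so there is no planned figure to reproduce. The check is a reading of the text, followed by arithmetic on an assumed loss.

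**Step 1. Which read supplies the pre value?** SAP 5.6.2 does not say outright. Three points favour the separate Pre read:
- Protocol 8.4.6 treats Pre and Paired as two modalities and keeps them apart: "Various modalities of images from the same patient will not be presented in the same batch". The SAP forms its LBR means by modality.
- Protocol 8.4.9 describes lesion matching between these two modalities as a separate tracking step. The SAP uses the same matching term for pre-contrast lesions.
- If the pre value came from within the Paired set, pre and post would belong to one lesion by construction and no matching would be needed.

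**Step 2. Can a lesion be matched between agents but absent from the Pre read?** Yes. Under protocol 7.1.1 the Pre reader chooses the largest potentially enhancing lesions, and the Paired reader gives priority to the largest that do enhance. A lesion unseen before contrast, or displaced by a different choice of three, has no Pre-read record. FAS2 still admits the patient.

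**Step 3. What happens in the model?** The SAP code is `model eval = GBCA period pre`. A record with `pre` missing is excluded. Each patient has two records, one per agent:
- no Pre match at either examination: both records go, and the patient is lost;
- a Pre match at one examination only: one record goes, and an unpaired record remains;
- three agent-matched lesions, one of them on the Pre read: the record stays, but the outcome averages three lesions and the covariate averages one, unless the restriction is also applied to the outcome.

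**Step 4. Comparison with E%.** E% = 100 × (SI post − SI pre) / SI pre, so it needs the pre-injection lesion signal. The SAP computes it for all agent-matched lesions, and Table 2 places it on the Paired sets only. Two signal-intensity measures, both analysed in FAS2, thus follow different lesion rules.

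**Step 5. Size.** Let f be the share of patients lost entirely. The documents do not give f, so the values below are assumptions. The base of 200 is the evaluable number planned for objective 2. The standard error is multiplied by 1/√(1 − f).

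| f (assumed) | Patients lost (200 × f) | SE factor |
|---|---|---|
| 5% | 10 | 1/√0.95 = 1.026 |
| 10% | 20 | 1/√0.90 = 1.054 |
| 20% | 40 | 1/√0.80 = 1.118 |

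As a check, simulated crossovers of 200 patients with records lacking a pre value removed kept 187 and 158 patients at nominal f of 10% and 20%. The SE ratios were 1.03 and 1.11, against 1/√(187/200) = 1.03 and 1/√(158/200) = 1.13. Loss there was at random, so this illustrates precision only.

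**The case against.** The best defence is that the SAP never names the Pre read as the source. If signal intensity is measured inside the Paired set, as Table 2 indicates, every agent-matched lesion has a pre value. The sentence would then remove only unmatched lesions, and nobody in FAS2 would be lost. The E% rule suggests the pre lesion signal is indeed recorded there. Reading details are left to the Blinded Image Evaluation Charter, which is not among the documents. This stands as a limit on certainty, but it does not settle the matter: the wording by modality and the matching condition fit the separate read better, and two statisticians could program the sentence differently.

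A reader might also infer a large loss from the roughly 68 patients without a valid primary criterion (protocol Amendment 2 rationale; SAP section 4). Against 245 − 25 = 220 patients that is 31%, which would give 1/√0.69 = 1.20. The documents do not support this use. SAP 3.3 ties the non-valid rate to criteria 1 and 2 together, the 68 are not split by cause, and any patient with no agent match for any reader is already outside FAS2.

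A reader might further infer that the rule biases the result towards one agent or shrinks a true difference. At each visit the Pre images are acquired before that visit's injection, in a randomised crossover with blinded readers. Visibility on the Pre read therefore cannot depend on the agent injected afterwards. The estimated difference would shrink only if the agents differed mainly in lesions invisible before contrast, and nothing in the documents establishes that. Many lesions may also be visible without contrast: protocol 8.2.2 calls for T2-weighted imaging in several regions, and section 1.2 describes most liver masses as easy to see unenhanced.

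Finally, LBR is one secondary criterion among many, and E% still compares agent-matched lesions without this restriction. That is correct and limits the consequence.

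**Conclusion.** The point holds as an inconsistency between the SAP's LBR rule, protocol Table 2 and the SAP's own E% rule. On the most natural reading, FAS2 records without a Pre-read match leave the LBR model, and partly matched patients can have pre and post means over different lesions. The harm is lost precision and a comparison narrowed towards lesions visible without contrast. It is not bias towards an agent, and neither primary objective is affected.

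The size is unknown. Under the assumption that 5% to 20% of patients are lost entirely, the standard error widens by about 3% to 12%. Because deletion is per record, the true pattern may be a mix of lost patients and unpaired records. The conclusion rests on reading the pre-contrast lesions as those of the separate Pre read, which the SAP implies but does not state.

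**What to change.** In SAP 5.6.2:
- take the pre-injection lesion and background signal from the unenhanced images within each Paired set, for every lesion matched between gadopiclenol and gadobutrol;
- delete the sentence that requires a match to pre-contrast lesions;
- state that the pre and post patient means are computed over the same lesions.

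If the pre background signal was not recorded on the Paired read, say so. In that case add the LBR comparison of protocol 11.3.6 without the pre covariate on all agent-matched lesions, and report the records lost from the covariate model for each reader and agent.

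The cost is SAP wording and programming. No new reads are needed if the Paired-set pre signals were captured, as Table 2 and section 7.2.9 imply. The downside is that the pre value is then measured with the enhanced images on view.

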### **Overall diagnostic preference**

For each off-site reader, the overall diagnostic preference will be tabulated and gadopiclenol will be compared to gadobutrol by a Wilcoxon signed-rank test.

The SAS® procedure used for this analysis will be:

```
proc univariate data=XXX;
  class reader;
  var pref;
  output out=XXX probs=PROBS;
run;
```

The reason of this preference will be displayed according to the contrast agent preferred.

Listing of efficacy data will be presented in CSR appendix 16.2.6.

### **5.7. Safety Evaluation**

The safety evaluation will be presented using the Safety Set except otherwise specified.

#### **5.7.1. Extent of Exposure**

Time between inform consent signed and 1st IMP administration, 1st and 2nd IMP administrations, 2nd injection of contrast agent and patient's last contact and inform consent signed and patient's last contact in days, volume actually administered, actual injection rate, location of injection site, mode of injection, injection of saline flush and occurrence of an overdose will be tabulated. Frequency tabulation of actual

CONFIDENTIAL	STATISTICAL ANALYSIS PLAN PHASE III TRIAL GDX-44-011 VERSION NO. 2.0      DATED 25 JANUARY 2021	████████ Page 40 / 57
--------------	---	--------------------------

injection rate according to following classes: <2 mL/s, between 2 and 3 mL/s including, >3mL/s will be also displayed per contrast agent group.

Listing of exposure will be presented in CSR appendix 16.2.5.

### 5.7.2. Adverse Events

AEs will be described systematically in terms of number and percentage of patients with AEs and in terms of number of AEs. AEs will be displayed by periods (MRI 1 and MRI 2) and overall.

AEs emergence will be defined as follows:

- Non-treatment emergent AE (NTEAE): if the AE starts prior to the 1st injection (pre-injection) or if the patient is not injected.
- Treatment emergent AE (TEAE): if the AE starts after the 1st injection (post-injection).
  - If it starts between the 1st injection and the 2nd injection (<), then it will be considered as a TEAE associated with the 1st contrast agent of the patient's series (MRI 1).
  - If it starts after the 2nd injection (≥), then it will be considered as a TEAE associated with the 2nd contrast agent of the patient's series (MRI 2).

Time to onset of AE will be calculated as follow: datetime of AE start – datetime of last start time of IMP administration before AE

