3.3 Trial Duration

3.3.1 *Duration of patient's participation*

Minimum trial duration for patients: 4 days, if V1 and V2 are done on the same day and the second MRI is done 2 days after the first one.

Maximum trial duration for patients: 23 days, if the screening period lasts 7 days and the second MRI is done 14 days after the first one.

The trial includes a maximum of 5 visits:

- One screening visit (V1) up to 7 days prior to inclusion (V1) could be done the same day as the randomization visit (V2) if all the inclusion/non-inclusion criteria are met).
- Two sequential imaging visits (V2 and V4, minimum interval 2 days and up to 14 days): each visit will consist of gadopiclenol injection or gadobutrol injection and MRI procedure.
- Two safety visits (V3 and V5): 1 day after each injection and MRI examination.

3.3.2 *End of trial*

The trial is considered as completed once all the images collected for all the patients have been reviewed by all the independent blinded readers.

The patient's participation is defined as the period from the screening visit (ICF signature) to the last trial visit.

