* The events which occur before the first IMP administration, and which are not serious and not related to the trial procedures, might be recorded as medical history upon the investigator's judgement.

** see the period of collection described in section 9.3.2

As reminder the patient's participation is defined as the period from the screening visit (ICF signature) to the last trial visit in the general case and defined in [Section 10](#) in case of premature discontinuation.

Any AE is followed-up from its onset to recovery or stabilization of sequelae. If no follow-up is performed, the investigator must provide a justification in the medical file and clinical eCRF.

9.1.3 *Description of Adverse Events*

The following guidelines and definitions should be used by the investigator for the description of an AE when reporting information in clinical eCRF and any specific AE report forms:

- **Nature (diagnosis) of AE:** preferably an overall diagnosis or syndrome, rather than individual symptoms or signs. The investigator must report AE using standard medical terminology. The same terms should be used in the source documentation and in the clinical eCRF.
- **Date and time of onset:** date and clock time of the AE start.
- **Intensity:**
 - Mild: the patient is aware of the sign or symptom, but it does not interfere with her/his usual daily activities and/or it is of no clinical consequence
 - Moderate: the AE interferes with the usual daily activities of the patient or it is of some clinical consequence
 - Severe: the patient is unable to work normally or to carry out his/her usual daily activities, and/or AE is of definite clinical consequence.
- **Date of the event end (or consolidation):** This date is the date when the event has come to its ends or to its initial intensity (for the events that had been an aggravation of a pre-existing disorder). If the AE is still ongoing by the time of end of trial follow-up for the patient (i.e. last trial visit), the patient should be followed-up until AE resolution or a justification should be provided by the Investigator (i.e. chronic disease) in the medical file.

 CONFIDENTIAL	Protocol No. GDX-44-011 Version No. 3.0 (including amendment 2) June 30, 2020	Page 55 / 82
---	---	--------------

- **Causal relationship to the Investigational Medicinal Product:**

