Non respect of study's schedule and procedures	MRI examination with gadopiclenol not performed	Clinical data base	Major
	MRI examination with gadobutrol not performed	Clinical data base	Major criteria2
	Time between the two MRI procedures is strictly greater than 14 days and less or equal to 21 days	Clinical data base	Non major
	Time between the two MRI procedures is strictly greater than 28 days	Clinical data base	Major criteria2
	Two different MRI system manufacturer used for both assessments of the same patient	Clinical data base	Non major
	Two different magnetic field strength used for both assessments	Clinical data base	Major criteria2
	MRI machine used not qualified	Monitoring	Non major
	Body region is different between the two MRs	Clinical data base	Non major
	US patients with an indication other than Breast MRI	Clinical data base	Non major
	Physical examination not performed	Clinical data base	Non major
	eGFR method is not the same throughout the trial	Clinical data base	Non major
	eGFR method is not accurate	Clinical data base	Non major
	Time between screening visit and first contrast agent administration is strictly greater than 7 days	Clinical data base	Non major
	Blood sample for central laboratory assessment is not drawn in the time window allowed by protocol	Clinical data base	Non major
	Vital sign is not measured in the time window allowed by protocol	Clinical data base	Non major
	Tolerance at injection site is not measured in the time window allowed by protocol	Clinical data base	Non major
	Last contact is not between 7 and 14 days after the last injection of IMP for patients recruited in France	Clinical data base	Non major
	Deviation in IWRS Process	Monitoring	Non major
	Clinical protocol procedure not respected	Monitoring	Non major
GCP deviation	Deviations related to ICF signature process	Monitoring	Non major
	Source document management not appropriate	Monitoring	Non major

Patients presenting at least one protocol deviation with a status "**Major**" will be excluded from the PPS1 and PPS2.

Patients presenting at least one protocol deviation with a status "**Major criteria1**" will be excluded from the PPS1

Patients presenting at least one protocol deviation with a status "**Major criteria2**" will be excluded from the PPS2

Frequency and percentages of patients with protocol deviations will be presented breaking down by status (major/non major).

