### TEAEs

The same table will be displayed by contrast agent groups and periods for Treatment Emergent AEs (TEAEs). The terms “NTEAE” will be replaced by “TEAE”. The following variables will be presented in addition:

- TEAEs with causal relationship to the IMP.
- TEAEs leading to discontinuation of the IMP.
- TEAE leading to IMP unblinding

Same analyses will be repeated by body regions.

The number and percentage of patients with at least one TEAE and the number of TEAE will be presented by contrast agent groups and period and overall according to Primary SOC and PT.

The table will be sorted by descending frequency of SOC and, within each SOC by descending frequency of PT according to the Total column.

Same analyses will be repeated by body regions.

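### TEAEs are attributed over 2 to 14 days after the first injection but mostly about 1 day after the second, so MRI 1 and MRI 2 percentages are not comparable and pooled by-agent percentages depend on when V4 is scheduled

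*SAP*

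**What the plan says.** **Attribution.** SAP 5.7.2 splits treatment-emergent events by injection order. For the first agent: "If it starts between the 1st injection and the 2nd injection (<), then it will be considered as a TEAE associated with the 1st". For the second: "If it starts after the 2nd injection (≥), then it will be considered as a TEAE associated with the 2nd contrast agent". No upper limit in days is given for either.

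**Schedule.** Protocol 3.3.1 gives "Two sequential imaging visits (V2 and V4, minimum interval 2 days and up to 14 days", and "Two safety visits (V3 and V5): 1 day after each injection and MRI examination".

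**Collection.** Protocol 9.1.2 states that "the patient's participation is defined as the period from the screening visit (ICF signature) to the last trial visit". Table 4 in that section has unrelated events collected up to the last follow-up visit. After the end of participation only related events and pregnancies are marked. The SAP deviation list also contains this entry: "Last contact is not between 7 and 14 days after the last injection of IMP for patients recruited in France". The amendment for France that the SAP cites is not among the supplied documents.

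**Display.** Under TEAEs the SAP says: "The same table will be displayed by contrast agent groups and periods for Treatment Emergent AEs (TEAEs"). The tables give counts and percentages of patients, and the overview and SOC/PT tables are repeated by body region. SAP 5.7.2 also derives a delay for each event ("Time to onset of AE will be calculated as follow: datetime of AE start" minus the last preceding administration). SAP 5.7.1 tabulates the time between the two administrations and from the second injection to last contact. The adverse event table list in SAP 6.1.3.2 has no table using a common window, time to onset or time at risk.

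**The concern.** An unrelated event on day 5 after an agent is a TEAE for that agent if it was given first and V4 has not yet taken place. If the agent was given second, the same event falls after V5 and is normally not collected. The two periods therefore count events over windows of different length.

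Two planned outputs are affected. The MRI 1 and MRI 2 columns will differ even if neither agent causes any event. And the absolute percentage for an agent over both periods, which serves the secondary objective of describing each agent's safety profile, becomes an average over a long and a short window whose value depends on how sites schedule V4. A reader of the planned tables cannot correct for this without rebuilding a common window from the patient listings.

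**Working it through.** **1. Confirm the 1-day tail from the plan's own figures.** Protocol 3.3.1 states a minimum of 4 and a maximum of 23 days per patient. Counting inclusively:
- minimum = 0 (screening) + 2 (gap) + 1 (V5) + 1 = 4 days;
- maximum = 7 + 14 + 1 + 1 = 23 days.

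Both agree, and both need follow-up to end 1 day after the second injection.

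**2. Window lengths.** Period 1 is 2 to 14 days and period 2 is 1 day, a ratio of 2:1 to 14:1. The share of a completer's time at risk lying in period 1 is 2/3 = 67% to 14/15 = 93%. The first window can exceed 14 days: SAP 5.2 treats a longer interval as a protocol deviation, while the Safety Set keeps everyone with at least one injection.

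**3. Effect on percentages.** The documents give no background event rate, so this is an assumption: a constant rate r per day, equal for both agents, with no drug effect. The proportion with at least one event in a window of w days is 1 − exp(−r·w). The pooled by-agent figure with 1:1 order and complete crossover is the mean of the two periods.

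| Assumed r per day | Period 1, 2-day gap | Period 1, 14-day gap | Period 2, 1 day | Pooled by agent |
|---|---|---|---|---|
| 0.5% | 1.0% | 6.8% | 0.5% | 0.75% to 3.6% |
| 1% | 2.0% | 13.1% | 1.0% | 1.5% to 7.0% |
| 2% | 3.9% | 24.4% | 2.0% | 2.95% to 13.2% |

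The ratio of period 1 to period 2 runs from about 2 to between 12 and 14, whichever rate is assumed. The 14-day column needs every patient at the maximum interval.

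**4. Between agents.** With equal order counts, intervals and retention, the pooled figure is identical for both agents. Two illustrations of imbalance, both at 1% per day and a 14-day gap:
- *Drop-out from one series only, 30 of 150 before the second injection.* Agent given first in that series: (150 × 13.06 + 150 × 1.00)/300 = 7.0%. The other agent: (150 × 13.06 + 120 × 1.00)/270 = 7.7%.
- *A 25-patient body region split 16:9 by order.* (16 × 13.06 + 9 × 1.00)/25 = 8.7% against (9 × 13.06 + 16 × 1.00)/25 = 5.3%. The minimum of 25 is the protocol's figure for thorax, pelvis and musculoskeletal. Protocol 5.3.1 describes blocks but states no stratification by region.

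**5. France.** If all events were collected to the 7-to-14-day contact, the period 1 to period 2 ratio would run from 2:14 (1:7) to 14:7 (2:1). This is an inference: the deviation entry fixes the date of contact and does not say which events are collected up to it.

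**6. With a common 1-day window.** At 1% per day both periods would show about 1.0%.

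**The case against.** The strongest reply is that nothing here favours either agent by design. Order is randomised 1:1, so each agent receives the same planned mix of long and short windows, and the SAP already shows agents within period, where the planned window is the same. No formal safety test or period contrast is planned. The intervals are tabulated in SAP 5.7.1. Events within 1 day of injection are scheduled to be captured equally after both injections, and related events remain reportable after V5, so the related-TEAE tables are less affected.

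All of that stands. A reader might infer that the rule biases the safety comparison between gadopiclenol and gadobutrol. The documents do not support this: even 30 patients lost from one series alone moves the illustration only from 7.0% to 7.7%.

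A reader might also infer that background events swamp an acute difference. If they are independent of the agent, about 12% of period 1 patients (1 − exp(−0.13)) have one after day 1 in the 14-day, 1%-per-day case. The pooled absolute difference then shrinks by about half of that, 6%.

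It may be tempting to conclude that a 1-day window should replace the main table. Protocol 7.2.11 defines post-contrast kidney injury over 48 to 72 hours and creatinine is checked again before V4, so a 1-day main table would set aside events of interest.

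The reply does not cover three things. The period columns are planned outputs that order balance does not protect. The absolute pooled percentages still depend on scheduling. And balance between series is not assured: 25 of 245 enrolled patients had already dropped out at Amendment 2, and the SAP plans for unequal drop-out between series only in the efficacy analysis.

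**Conclusion.** The point holds as a limit on interpretation. MRI 1 and MRI 2 TEAE percentages cannot be compared as tabulated, and pooled by-agent percentages depend on V4 scheduling. The window ratio of 2:1 to 14:1 follows from the documents for unrelated events under the global schedule. The percentages (2.0% to 13.1% against 1.0%) rest on an assumed constant rate of 1% per day with no drug effect.

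The between-agent contrast is balanced by design. It is disturbed only if order counts, V2 to V4 intervals or drop-out differ between series or within small body-region subgroups. A further difference in windows for French patients is plausible but cannot be confirmed from the supplied documents. This is a cheap improvement: CONSIDER.

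**What to change.** - Keep the all-TEAE tables as the main tables.
- Add by-agent and by-period TEAE tables limited to onset from injection to the 1-day safety visit (V3 or V5). This window is scheduled after both injections and is shorter than the minimum 2-day gap. The onset date and clock time are already collected and time to onset is already derived.
- Show later-onset TEAEs separately, with number of patients and days at risk by agent and period, and with France identified separately.
- State in SAP 5.7.2 that all-TEAE percentages are not to be compared between MRI 1 and MRI 2.

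The cost is SAP wording and one extra set of tables, with no new data. The downside is that the added tables must be read alongside the main ones, because events after 1 day, such as delayed creatinine changes, appear only in the all-TEAE and later-onset tables.
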